10.1 Protection of Personally Identifiable Information

Abbott respects and protects personally identifiable information collected or maintained for this clinical investigation. The privacy of each subject and confidentiality of his/her information will be preserved in reports and when publishing any data. Confidentiality of data will be observed by all parties involved at all times throughout the clinical investigation. All data will be secured against unauthorized access.

10.2 Data Management Plan

A Data Management Plan (DMP) will describe procedures used for data review, database cleaning, and issuing and resolving data queries. If appropriate, the DMP may be updated throughout the clinical investigation duration. All revisions will be tracked and document controlled.

Subject data will be captured in a validated electronic data capture (EDC) system hosted by the Sponsor. CRF received data for the clinical investigation will be entered by trained Abbott personnel. An electronic audit trail will be used to track any subsequent changes of the entered data.

10.3 Document and Data Control

10.3.1 Traceability of Documents and Data

The investigator will ensure accuracy, completeness legibility and timeliness of the data reported to the Sponsor on the CRFs and in all required reports.

10.3.2 Recording Data

The CRFs will be signed and dated by the authorized site personnel. Any change or correction to data reported on a paper CRF will be dated, initialed and explained if necessary, and will not obscure the original entry.

11 Monitoring

It is the responsibility of the Sponsor to ensure the clinical investigation is conducted, recorded and reported according to the approved CIP, subsequent amendment(s), applicable regulations and guidance documents.

Centralized monitoring will occur through routine internal data review. This monitoring is designed to identify missing and inconsistent data, data outliers, and potential CIP deviations that may be indicative of site non-compliance. On-site monitoring may occur at the discretion of the Sponsor.

12 Compliance Statement

12.1 Statement of Compliance

This clinical investigation will be conducted in compliance with the most current regional and local laws and regulations. Principles of Good Clinical Practice will be followed as based on the most current version of the World Medical Association (WMA) Declaration of Helsinki.

The investigator will sign a Clinical Trial Agreement and agrees to be compliant with it. The investigator will not start enrolling subjects or requesting informed consent from any subject prior to obtaining IRB/EC approval and relevant Regulatory Authority approval, if applicable, and authorization from the Sponsor in

writing for the clinical investigation. If additional requirements are imposed by the IRB/EC or relevant Regulatory Authority, those requirements will be followed. If any action is taken by an IRB/EC or a relevant Regulatory Authority with respect to the clinical investigation, that information will be forwarded to the Sponsor.

As the Sponsor, Abbott has taken up general liability insurance in accordance with the requirements of the applicable local laws. An appropriate Abbott country representative will be utilized to understand the requirements for the type of insurance that will be provided for subjects, and such information will be incorporated into the site informed consent, as applicable. If required, additional subject coverage or a clinical investigation specific insurance will be provided by the Sponsor.

12.2 Quality Assurance Audits and Regulatory Inspections

The investigator and/or delegate should contact the Sponsor immediately upon notification of a regulatory authority inspection at the site. A monitor or designee will assist the investigator and/or delegate in preparing for the audit. The Sponsor may perform quality assurance audits, as required.

The Principal Investigator or institution will provide direct access to source data during and after the clinical investigation for monitoring, audits, IRB/EC review and regulatory authority inspections, as required. The Principal Investigator or institution will obtain permission for direct access to source documents from the subject, hospital administration and national regulatory authorities before starting the clinical investigation.

12.3 Repeated and Serious Non-Compliance

In the event of repeated non-compliance or a one-time serious non-compliance, as determined by the Sponsor, a monitor or designee will attempt to secure compliance by one or more of the following actions:

- Visiting the investigator,
- Contacting the investigator by telephone,
- Contacting the investigator in writing,
- Retraining of the investigator.

If an investigator is found to be repeatedly non-compliant with the signed agreement, the CIP or any other conditions of the clinical investigation, the Sponsor will either secure compliance or, at its sole discretion, terminate the investigator's participation in the clinical investigation. In case of termination, the Sponsor will inform the responsible regulatory authority, as required, and ensure that the IRB/EC is notified, either by the Principal Investigator or by the Sponsor.

13 Suspension or Premature Termination of the Clinical Investigation

The Sponsor reserves the right to terminate the clinical investigation at any stage, with appropriate written notice to the investigators, IRB/ECs and relevant Regulatory authorities, if required.

A Principal Investigator, IRB/EC or regulatory authority may suspend or prematurely terminate participation in a clinical investigation at the investigational sites for which they are responsible. The investigators will follow the requirements specified in the Clinical Trial Agreement.

If suspicion of an unacceptable risk to subjects arises during the clinical investigation or when so instructed by the IRB/EC or regulatory authority, the Sponsor may suspend the clinical investigation while the risk is assessed. The Sponsor will terminate the clinical investigation if an unacceptable risk is confirmed. If the Sponsor completes an analysis of the reasons for the suspension, implements the necessary corrective actions, and decides to lift the temporary suspension, the Sponsor will inform the Principal Investigators, IRB/EC, or regulatory authority, where appropriate, of the rationale, providing

them with the relevant data supporting this decision. Approval from the IRB/EC or regulatory authority, where appropriate, will be obtained before the clinical investigation resumes. If subjects have been informed of the suspension, the Principal Investigator or authorized designee will inform them of the reasons for resumption.

If the Sponsor suspends or prematurely terminates the clinical investigation at an individual investigational site in the interest of safety, the Sponsor will inform all other Principal Investigators.

If suspension or premature termination occurs, the Sponsor will remain responsible for providing resources to fulfill the obligations from the CIP and existing agreements for following up the subjects enrolled in the clinical investigation, and the Principal Investigator or authorized designee will promptly inform the enrolled subjects at his/her investigational site, if appropriate.

14 Clinical Investigation Conclusion

The clinical investigation will be concluded when:

- All sites are closed AND
- The final report has been provided to investigators or the Sponsor has provided formal documentation of clinical investigation closure.

15 Publication Policy

Publications or presentations of clinical investigation methods or results will adhere to Abbott's publication policy, which is based on Good Publication Practices and International Committee of Medical Journal Editors (ICMJE) guidelines. A copy of the policy will be provided upon request of the investigator.

Appendix A: CIP Revisions

Procedure for CIP Amendments

This CIP may be amended as appropriate by the Sponsor. Rationale will be included with each amended version in the revision history table below. The version number and date of amendments will be documented.

The acknowledgement of the amended CIP by the Coordinating Investigator (if applicable) and the Principal Investigators will be collected on the signature pages.

IRB/EC and relevant Regulatory Authorities, if applicable, will be notified of amendments to the CIP.

Revision History								
Amendment	Version	Date	Rationale	Details				
Number								
Not	VA	ddMMMyyyy	First release of CIP	NA				
Applicable								

Appendix B: Definitions

Non-study Specific Definitions

Adverse Event (AE)

Any untoward medical occurrence, unintended disease or injury, or untoward clinical signs (including abnormal laboratory findings) in subjects, users or other persons, whether or not related to the investigational medical device under clinical investigation.

This definition includes events related to the investigational medical device or the comparator. This definition includes events related to the procedures involved.

Serious Adverse Event (SAE)

An adverse event that led to:

- Death
- A serious deterioration in the health of the subject, that either resulted in:
 - A life-threatening illness or injury OR
 - A permanent impairment to a body structure or a body function OR
 - o An in-patient or prolonged hospitalization OR
 - A medical or surgical intervention to prevent life-threatening illness or injury or permanent impairment to a body structure or a body function OR
- Fetal distress, fetal death or a congenital abnormality or birth defect

A planned hospitalization for a pre-existing condition, or a procedure required by the CIP is not considered a serious adverse event.

Adverse Device Effect (ADE)

An adverse event related to the use of an investigational medical device.

This definition includes adverse events resulting from insufficient or inadequate instructions for use, deployment, implantation, installation, or operation, or any malfunction of the investigational medical device.

This definition includes any event resulting from the use error or from intentional misuse of the investigational medical device.

Serious Adverse Device Effect (SADE)

Adverse device effect that has resulted in any of the consequences characteristic of a serious adverse event.

Unanticipated Adverse Device Effect (UADE)

As defined in 21 CFR §812.3, unanticipated adverse device effects (UADE) are defined as any serious adverse effect on health or safety or any life-threatening problem or death caused by, or associated with, a device, if that effect, problem, or death was not previously identified in nature, severity, or degree of incidence in the CIP or application (including a supplementary plan or application), or any other unanticipated serious problem associated with a device that relates to the rights, safety, or welfare of subjects.

Anticipated Serious Adverse Device Effect (ASADE)

A serious adverse device effect which by its nature, incidence, severity or outcome has been previously identified in the risk analysis report.

Unanticipated Serious Adverse Device Effect (USADE)

A serious adverse device effect which by its nature, incidence, severity or outcome has not been identified in the current version of the risk analysis report.

Device Deficiency (DD)

A Device Deficiency is defined as an inadequacy of a medical device with respect to its identity, quality, durability, reliability, safety or performance. Device deficiencies include malfunctions, use errors and inadequate labeling.

Vulnerable Subject

Vulnerable subject is defined as individual whose willingness to volunteer in a clinical investigation could be unduly influenced by the expectation, whether justified or not, of benefits associated with participation or of retaliatory response from senior members of a hierarchy in case of refusal to participate. *EXAMPLE Individuals with lack of or loss of autonomy due to immaturity or through mental disability, persons in nursing homes, children, impoverished persons, subjects in emergency situations, ethnic minority groups, homeless persons, nomads, refugees, and those incapable of giving informed consent. Other vulnerable subjects include, for example, members of a group with a hierarchical structure such as university students, subordinate hospital and laboratory personnel, employees of the Sponsor, members of the armed forces, and persons kept in detention.*

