5.4.1 Inclusion Criteria

- Subject is able to provide informed consent to participate in the study;
- Subject diagnosed with chronic intractable pain associated with back and/or limbs;
- Subject is 18 years of age or older;
- Subject has failed to respond to at least 6 months of conventional treatment which may include pharmacological treatment, physical therapy, epidural injections;
- Subject has a back and/or leg pain intensity of at least 6.0 cm out of 10.0 cm on the average back and/or leg pain VAS at baseline;
- Subject's medical record has been evaluated by the Investigator to ensure that the subject is a
 good candidate for a neurostimulation system;
- Subject is on stable pain medications with a total opioid for at least 28 days prior to enrolling in this study, and is willing to stay on those medications with no dose increase until the 3 month visit;
- Subject is willing to cooperate with the study requirements including compliance with the regimen and completion of all office visits;
- Female candidates of child-bearing potential agree to commit to the use of an effective method of contraception (including but not limited to sterilization, barrier devices, oral contraceptives, intrauterine devices (IUDs), condoms, rhythm method, or abstinence) for the duration of the study

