9.2 Safety Reporting

Safety surveillance within this study and the safety reporting performed both by the investigator and Sponsor starts as soon as the procedure begins. This is defined as from the time the [dilator/device delivery system has been introduced into the body.

The safety surveillance and the safety reporting will continue until the last investigational visit has been performed, the subject is deceased, the subject/investigator concludes his participation into the clinical investigation or the subject withdrawal from the clinical investigation.

All adverse event data including deaths and device deficiency data (if applicable) will be collected throughout the clinical investigation and will be reported to the Sponsor on a CRF.

Adverse events will be monitored until they are adequately resolved or the subject has ended his/her participation in the trial, whichever comes first. The status of the subject's condition should be documented at each visit.

The investigator will report the event to the IRB/EC per their reporting requirements.

Reportable events to sponsor are considered:

- All Adverse Device Effects
- All Serious Adverse Events (whether or not the event is considered device or procedure related and regardless the randomization group)
- (if applicable) device deficiencies, that could have led to a serious adverse device effect
 - if either suitable action had not been taken;
 - if intervention had not been made or
 - if circumstances had been less fortunate

All events mentioned above will be reported to the Sponsor, as soon as possible, but no later than 72 hours of first learning of the event.

Reportable events shall be submitted to the Sponsor. The Sponsor will ensure that all applicable events and device deficiencies are reported to the relevant authorities as per regulations. The sites should notify the Sponsor of reportable adverse events.. Additional information may be requested by the Sponsor in order to support the reporting of AEs to regulatory authorities. The investigator must notify the IRB/EC, if appropriate, in accordance with national and local laws and regulations, of the AEs reported to the Sponsor. All adverse events will be reported as per applicable regulatory requirements.

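### The SAE exclusion for planned hospitalization has no limit on date or worsening, so an admission for seriously worsened study pain, judged not device-related, could be classed as non-serious

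*Combined protocol and SAP*

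**What the plan says.** Appendix B defines an SAE by outcome. Apart from death and fetal outcomes, the entry condition is "A serious deterioration in the health of the subject, that either resulted in" one of several listed results, and hospital admission is among them: "An in-patient or prolonged hospitalization OR". The definition then ends with the exclusion at issue: "A planned hospitalization for a pre-existing condition, or a procedure required by the CIP is not considered a serious adverse event".

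A serious adverse device effect (SADE) is defined separately in the same appendix: "Adverse device effect that has resulted in any of the consequences characteristic of a serious adverse event". The exclusion is not repeated there.

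Section 9.2 lists what must go to the sponsor quickly. The list includes "All Adverse Device Effects" and "All Serious Adverse Events (whether or not the event is considered device or procedure related and regardless the randomization group"), both due "no later than 72 hours of first learning of the event". The remaining item is certain device deficiencies. Other adverse events are collected on a case report form, and Section 9.2 sets no 72-hour limit for them.

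Section 5.4.1 makes the study condition an entry requirement: "Subject diagnosed with chronic intractable pain associated with back and/or limbs".

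**The concern.** An exclusion for planned admissions normally keeps events out of the SAE count when they were going to happen anyway and say nothing about the study treatment. This sentence does not confine itself to those events. It names no date before which the admission must have been planned, and it does not require the condition to be stable.

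In many trials that would be a small looseness. Here the condition being treated is a pre-existing condition in every subject, so the exclusion can reach the disease under study. An admission booked during follow-up because the pain had become seriously worse is planned in the everyday sense, and it is for a condition that existed before the study.

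Loss of pain control is also a natural safety question for this therapy. In both trial-phase patterns stimulation is off for three quarters of the time: 90 / (30 + 90) = 75% and 15 / (5 + 15) = 75%. If the 1:12 ratio of Program 1 means one part on to twelve parts off, the off share is 12 / 13 = 92%.

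At stake is whether such an admission carries the serious label and reaches the sponsor within 72 hours, and whether sites decide this in the same way. Little later in the process would even out different readings. The body of the protocol describes no committee to adjudicate events, and Section 11 leaves on-site monitoring to the sponsor's discretion.

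**Working it through.** The documents give no figure on this point and no formula applies. The check is a reading of the definitions against each other.

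**Step 1: is the exclusion limited anywhere?** The places that bear on seriousness and reporting are the follow-up and unscheduled visits (Sections 6.4.6 and 6.6), the risk sections (Section 8 through 8.1.2), safety reporting, deaths and complaints (Sections 9.2 to 9.2.2) and Appendix B. None says when an admission must have been planned, and none deals with worsening of a pre-existing condition. The term planned is not defined.

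**Step 2: does the study pain count as pre-existing?** Yes, in every subject, because Section 5.4.1 requires it for entry.

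**Step 3: what happens to an admission for that pain?** The answer depends on when it was arranged, whether health seriously deteriorated, and whether the event is judged device-related.

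| Admission for the study pain | Main SAE rule | Exclusion read literally | Route to the sponsor if the exclusion applies |
|---|---|---|---|
| Booked before consent, pain unchanged | Not met | No effect | None needed |
| Arranged in follow-up, pain back but no serious deterioration | Not met | No effect | Adverse device effect within 72 hours if device-related; otherwise adverse event form |
| Arranged in follow-up, serious deterioration, judged device-related | Met | Could remove the SAE label | Adverse device effect within 72 hours; can still be a SADE |
| Arranged in follow-up, serious deterioration, judged not device-related | Met | Could remove the SAE label | Adverse event form, with no 72-hour limit |

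**Step 4: where does the wording make a difference?** In the first two rows the exclusion changes nothing. In the third it affects the label but not the speed of reporting. It also exposes a conflict: hospitalization is a consequence characteristic of an SAE, so the same event can be a serious device effect under one definition and not an SAE under the other. In the fourth row both the serious label and the expedited report can be lost.

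**Step 5: how firm is the relatedness judgment that separates the last two rows?** Section 8.1.1 names reduced pain relief as a device effect only as a result of lead migration. A site could reasonably attribute returning pain to the underlying disease. Section 9.2 makes SAEs reportable whatever their cause, which protects against that uncertainty, but the protection works only if the event is first called an SAE.

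**The case against.** The strongest reply is that the sentence is generic wording, under a heading that calls the definitions non-study specific, and that a sensible reader takes planned to mean planned before the subject entered the study. On that reading the fourth case above stays an SAE. This is a fair reading and it rules out any claim that such admissions are definitely not counted. It does not settle the matter, because the text supports the literal reading equally well and sites have nothing to choose by.

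The second reply is that hospitalization alone does not make an SAE; serious deterioration is required first. This stands. Pain that drifts back towards its baseline level without serious deterioration would not be an SAE even if the exclusion were deleted.

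The third reply is that the information is not lost. All adverse event data go on a case report form, device-related events reach the sponsor in 72 hours, and pain is scored at 1, 3 and 6 months as the primary outcome. This also stands, and it confines the effect to a label and a deadline for events judged unrelated to the device.

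The fourth reply is that the protocol answers inadequate relief by changing the stimulation parameters and mentions no admission. That is what Section 5.1 describes, but it does not rule out an admission during the six months of follow-up.

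A reader might also infer that complications of the implant procedures escape the SAE definition, since the same sentence exempts procedures the protocol requires. The documents do not support this. The exemption is for the procedure itself, and the adverse event definition in Appendix B expressly covers events related to the procedures involved.

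**Conclusion.** The wording gap is real and should be closed. An admission arranged after consent for serious deterioration of the study pain, judged not device-related, could be classed as non-serious and miss the 72-hour SAE report. It would still be collected as an adverse event. Separately, the SAE and SADE definitions treat the same device-related admission differently and need to be reconciled.

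The conclusion rests on two conditions: that a site reads planned to include elective admissions arranged during the study, and that the deterioration meets the existing threshold. Neither is certain for a given event.

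The size cannot be estimated. Up to 60 enrolled subjects all have the condition, but the documents give no rate of admissions, SAEs or permanent implants. Dividing one event by a number of subjects would show only the denominator, not an expected undercount. No SAE-rate endpoint, success criterion or statistical stopping rule depends on the count (Sections 5.3, 7.6 and 7.8).

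Two stronger readings should be resisted. A reader might infer that admissions for returning pain drop out of expedited reporting altogether; that fails for device-related events. A reader might also think the lack of a control arm makes the undercount undetectable, but a control arm under the same definition would lose the same kind of admission and would not reveal it.

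**What to change.** Amend the exclusion in Appendix B so that it applies only to a hospitalization planned before informed consent for a pre-existing condition, or to a procedure required by the protocol, in either case without serious deterioration in health since consent. Both limits are needed: a date alone would leave open an admission booked earlier for a condition that has since seriously worsened.

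Add that an admission arranged after consent because a pre-existing condition has worsened, including the study pain, is assessed against the existing SAE criteria. This does not make every such admission an SAE; it removes the automatic exemption and leaves the serious-deterioration threshold in place.

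State in the SADE definition whether the amended exclusion applies there too, so that one admission cannot be serious under one definition and not under the other.

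The cost is a few lines of text and matching site training. The downside is a few more SAE reports and a slightly less favorable SAE count. No treatment rule, visit or efficacy analysis changes.
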